Study recruitment occurs primarily in the hospital after the potentially eligible patients (those currently enrolled in the separate protocol AAAR7350 and interested in learning more about other research studies) have been admitted to the hospital and transferred to an inpatient bed. For some patients, study recruitment may occur post-discharge, up to 6 weeks following participants' presentation to the Emergency Department when they enrolled in the PHS study. Research coordinators for the present protocol will approach these patients, introduce the study and begin the informed consent process. Consenting participants are randomized to the intervention or control condition and complete baseline measures for the present protocol at the pre-training session (i.e., Time 1). Participants are given an electronic tablet device and a brief training on its use at the end of or within several days of this baseline session. For the subset of patients who provide signed consent and the brief tablet training for this intervention study in the hospital but who are then discharged prior to this session, the Time-1 session is conducted by phone while the patients are at home. An additional subset of patients who consent to participate in this study will come to CUMC after hospital discharge to conduct the questionnaires and the brief tablet training of the pre-training session (i.e., Time 1) in person. All participants then complete 8 sessions of the training (intervention or control version) at home twice per week for 4 weeks using the tablet. During this time their adherence to a heart medication is monitored using eCAP devices that they receive during enrollment or in the mail. For participants currently prescribed aspirin but no other heart medication, their adherence to aspirin will be monitored using the eCAP devices. For participants *not* currently prescribed aspirin but who *are* currently prescribed a heart medication other than aspirin, such as a non-aspirin antiplatelet, a beta-blocker, a statin, or an antihypertensive medication, their adherence to this other heart medication is monitored using the eCAP devices. Within several days following the completion of the 4-week training, participants are then contacted by phone for the post-training session (i.e., Time 2), during which they complete the same measures as completed at the Time-1 session. Then, participants return the tablet devices to CUMC researchers using pre-addressed envelopes/packages mailed to their homes. Finally, at 8 weeks after the Time-1 session, participants return the eCAP medication adherence monitoring devices to CUMC researchers also using pre-addressed envelopes/packages boxes.

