Control version: Participants are equally likely to receive positive or negative feedback for endorsing or rejecting threat interpretations or for endorsing or rejecting benign interpretations. For each administration of the task, the tendency to make threat interpretations is assessed as the proportion of threat endorsements (i.e., “Yes” responses) on trials with threat-related words, and the tendency toward benign interpretations is assessed as the proportion of benign endorsements on trials with benign words. Additionally, we will assess threat rejection time (i.e., mean speed of responding “No” on trials with sentences preceded by a threat-related word).

Measures

Fear of recurrence (FoR) of ACS. We have adapted the Concerns about Recurrence Scale (CARS)¹³ for ACS. This multidimensional scale was originally designed to measure fear of recurrence of breast cancer. This adapted scale comprises 26 items evaluating three specific components of FCR. The health worries subscale evaluates fears about declining health (e.g., “I worry that a recurrence of a heart problem would threaten my physical health”). The role worries subscale evaluates fears about impaired relationships with other

people (e.g., “I worry that a recurrence of a heart problem would keep me from fulfilling my responsibilities”). The death worries subscale evaluates fears about mortality (e.g., “I worry that a recurrence of a heart problem would threaten my life”). Each item is rated on a Likert scale ranging from 0 (not at all) to 4 (extremely). A total score can be obtained for each subscale and for the total scale by summing the items. A higher score indicates higher levels of FoR.

Future time perspective. An exploratory aim of the study is to determine the relationships among FoR and medication adherence with future time perspective. Patients with cardiac-induced PTSD often report that their sense of the future is foreshortened, and prior conceptualizations of PTSD emphasized this sense.⁷ This sense of a foreshortened future has been shown to strongly predict PTSD diagnosis in a population of patients with multiple sclerosis, and may be similarly associated with both PTSD and nonadherence in ACS patients.¹⁶

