To measure FoR in ACS patients, and test its associations with ACS-induced PTSD, diminished future time perspective, and nonadherence to medications.

We will test the extent to which the hypothesized measures of the behavior change mechanisms in question (FoR, future time perspective) are intercorrelated in ACS patients with elevated acute stress symptoms. First, to test convergent validity, we will assess zero-order correlations among these measures. Specifically, we predict that—across both groups at Time 1 before the intervention—higher FoR will be associated with lower future time perspective (i.e., lower FTPS). Second, we will test whether higher FoR is associated with higher threat perception symptoms and overall lower proportion of days adherent to aspirin. Third, due to the within-subjects design, we will also assess test-retest reliability from Time 1 to 2, both across and within groups. In this way we will ensure that we have valid and reliable measures of our proposed mechanisms of behavior change.

Specific Aim 2.

To test whether a cognitive-affective intervention reduces FoR in ACS patients.

We will conduct a univariate ANOVA to assess the effect of the four-week intervention on pre-to-post change in FoR, the proposed target mechanism. Prior intervention research in cancer patients showed a small to moderate effect size of a cognitive-affective intervention on FoR symptoms (Hedge's g for difference in health worries from pre- to post-intervention = 0.35). In separate unadjusted tests with pre-to-post change in FoR (and in an exploratory test of future time perspective) as the outcome, we will enter group (intervention, control) as the predictor. We will repeat the tests adjusting for factors that may explain variance in health behavior, including demographic information (age, sex, race, ethnicity), medical severity assessed by GRACE risk score¹⁸ and Charlson comorbidity index,¹⁹ and depressive symptoms assessed by PHQ-8 score.²⁰

Specific Aim 3.

To test whether patients randomized to the intervention are more adherent to aspirin in the 2-month monitoring period within the first several months after their suspected ACS event, and secondarily, whether any intervention effect is explained by reduced FoR.

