We will test this mediational hypothesis using conditional process modeling with the PROCESS macro in SPSS.²¹ Although we will likely have insufficient power to test the question definitively, the results will inform whether a future larger trial is warranted. The behavioral outcome in the model is heart medication adherence from the eCAP data: mean proportion of adherent days in the 2-month monitoring period that occurs within several months after hospital discharge. The predictor is group (intervention, control). The mediator is pre-to-post change in FoR from Time 1 to 2. For a secondary analysis, we will test the outcome as the magnitude of the slope of change in weekly proportion of adherent days during the 2 months. We will evaluate whether there is a significant indirect effect that supports the notion that the intervention vs. the control training engaged the target mechanism in such a way that changes in the target predicted improved heart medication adherence over the month-long intervention.

Exploratory Aim 1.

We will test for off-target intervention effects on future time perspective, as well as the alternative mediation path through improvement in future time perspective.

The test will be structured as for Specific Aim 3 but with pre-to-post change in future time perspective as the tested mediator.

Exploratory Aim 2.

We will test whether the intervention is associated with greater increases in physical activity relative to the control group and whether this association is mediated by changes in FoR or future time perspective.

The test will be structured as for Specific Aim 3 and Exploratory Aim 1 but with physical activity as the tested behavioral outcome measure instead of medication adherence.

Power analysis.

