In prior research with $N = 97$ at Time 1 using a similar intervention in cancer patients, a moderate effect size (Hedges $g = 0.54$) was found for differences in FoR between the intervention ($n = 64$) and control ($n = 36$) groups after 3 months and a somewhat smaller effect size (Hedge's $g = 0.35$) immediately after the 1-month intervention.¹³ Using G*Power 3.1,²² we tested a range of effect sizes for two levels of power. We determined that the present study is conservatively powered to change FoR in a fixed-effects one-way ANOVA with an effect size f of 0.35 or larger with a sample size of $N = 100$ (50 intervention, 50 control), given alpha = .05 and an intention-to-treat design in which missing data due to attrition are handled with multiple imputation.

4. Study Procedures

Patients will be considered for enrollment in the present study who are currently enrolled in AAAR7350 (the PHS study), who signed consent for AAAR7350 within the last 6 weeks (i.e., 42 days), who have indicated they are willing to hear about other research studies, and who have an Elevated Threat Perception score. Consent will be obtained using an IRB-approved consent form.

Pre-training/Time 1: For patients consenting to the study in the hospital, the pre-training session ideally occurs at this same visit. The RA will assess the potential mechanisms of behavior change verbally. At the end of this session, each patient will be given a tablet and an eCAP bottle with a brief explanation of their use. The estimated duration of this session is 45 minutes, including the consent process, questionnaires, and the brief training in the use of the tablet. A subset of patients will complete the consent process and receive the devices (eCAP bottle, tablet) with a brief training in the hospital and will then separately complete the questionnaires verbally by phone within several days. A separate subset of patients will complete the Time-1 session at CUMC sometime after hospital discharge but before 6 weeks (i.e., 42 days) have elapsed from the time of consent to the protocol AAAR7350.

Training phase: Random group assignment to the intervention or control group will be determined in a double-blind way by the programmed tasks on the tablet for each participant.

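### N = 100 is called conservatively powered for f = 0.35, but that is d = 0.70; on a common SD it is twice the cited immediate effect, for which power is about 41%

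*Combined protocol and SAP*

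**What the plan says.** All references are to the combined protocol and SAP.

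- **Section 3, Power analysis.** An earlier trial of a similar intervention in cancer patients is cited with Hedges g = 0.54 for FoR at 3 months and g = 0.35 "immediately after the 1-month intervention". The paragraph then concludes that "the present study is conservatively powered to change FoR in a fixed-effects one-way ANOVA with an effect size f of 0.35 or larger", with N = 100 (50 per arm) and alpha 0.05. Two levels of power are said to have been examined. Neither is named, no power value is reported, and no conversion between g and f is shown.
- **Section 3, Specific Aim 2.** The planned test is stated as: "We will conduct a univariate ANOVA to assess the effect of the four-week intervention on pre-to-post change in FoR". The unadjusted version has group as the predictor. The motivating effect is given as Hedges "g for difference in health worries from pre- to post-intervention = 0.35", described as small to moderate.
- **Section 2, Study Design.** Time 2 takes place "Within several days following the completion of the 4-week training".
- **Section 2, Measures.** For the FoR scale, "A total score can be obtained for each subscale and for the total scale by summing the items".
- **Section 3, Specific Aim 3.** A caveat appears here: "Although we will likely have insufficient power to test the question definitively". It refers to the mediation hypothesis.

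**The concern.** The number 0.35 appears first as a Hedges g and then as a Cohen f. These are different scales: for two equal groups an f of 0.35 is a standardised difference of 0.70. If both are in units of the same SD, the design effect exceeds both effects the paragraph cites, so the study cannot be called conservatively powered against them. The repeated number suggests that g was entered as f, but the documents do not say so and nothing below depends on it.

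This is the only sample-size calculation in the documents. Aim 2 asks whether the intervention moves its target, and change in FoR is also the mediator in Aim 3. A non-significant Aim 2 result, read beside this statement, could be taken as good evidence that the intervention does not produce the effect seen before, when the trial may have had less than an even chance of detecting it.

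**Working it through.** **Inputs from the documents.** One-way fixed-effects ANOVA with two groups; outcome pre-to-post change in FoR; N = 100, 50 per arm; alpha 0.05 (the F test is non-directional, so equivalent to a two-sided t test); design effect f = 0.35; cited effects g = 0.35 (immediate) and 0.54 (3 months). I treat g as d.

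**Which cited effect applies.** Time 2 falls within days of the end of the 4-week training, so the matching benchmark is g = 0.35.

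**Method.** For two equal groups f = d/2. Power is the upper tail of a noncentral F with 1 and N − 2 degrees of freedom and noncentrality λ = f²N.

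**The plan's own claim first.** With f = 0.35, λ = 0.1225 × 100 = 12.25 and power is 93%. For f = 0.35, a total of 68 gives 80% power and 88 gives 90%. Read literally, N = 100 is enough.

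**The cited effects, with d on the change-score SD:**

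| d | f = d/2 | λ | Power, N = 100 |
|---|---|---|---|
| 0.70 | 0.35 | 12.25 | 93% |
| 0.54 | 0.27 | 7.29 | 76% |
| 0.35 | 0.175 | 3.06 | 41% |

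Ratios: 0.70/0.35 = 2.0 and 0.70/0.54 = 1.3.

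**Detectable effect with N = 100.** 80% power: f = 0.283, d = 0.57. 90% power: f = 0.327, d = 0.65.

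**Smallest observed difference reaching p < 0.05.** t(0.975, 98) × √(2/50) = 1.984 × 0.2 = 0.40 SD, which is also the expected half-width of the 95% confidence interval. An observed difference of exactly 0.35 SD gives t = 0.35/0.2 = 1.75 and p = 0.08, so reproducing the cited effect exactly would miss significance.

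**If g is on the raw-score SD.** The documents do not name the SD that standardises g. Assuming equal SDs at the two times and a Time 1–Time 2 correlation r, the effect on the change score is d = g/√(2(1 − r)). The documents give no r; under Specific Aim 1 they say "we will also assess test-retest reliability from Time 1 to 2". Over an assumed range:

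| Assumed r | d for g = 0.35 | Power, g = 0.35 | Power, g = 0.54 |
|---|---|---|---|
| 0.3 | 0.30 | 31% | 62% |
| 0.5 | 0.35 | 41% | 76% |
| 0.6 | 0.39 | 49% | – |
| 0.7 | 0.45 | 61% | 93% |
| 0.8 | 0.55 | 78% | 99% |

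For g = 0.35, 80% power needs r = 1 − (0.35/0.566)²/2, about 0.81. For it to equal d = 0.70, r must be 1 − (0.35/0.70)²/2 = 0.875.

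**Attrition.** No dropout rate is given. As an illustration, at d = 0.35 on the change-score SD, power falls to 38% with 90 completers and 34% with 80.

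**The case against.** The strongest defence is that no stated figure is false. The sentence claims adequate power for f of 0.35 or larger, and N = 100 delivers 93%. If the two unnamed power levels were 80% and 90% (an assumption), the sample exceeds the requirement by 32 and 12 patients, and conservatively could mean just that. The comparison with the cited effects is drawn from neighbouring sentences.

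That reading is possible, but the paragraph opens with those effects and offers no other basis for f = 0.35. A margin over the requirement for an effect larger than anything cited is not conservative in a sense that helps a reader interpret Aim 2.

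A second defence is that the SD behind g is unknown, so the factor of two and the 41% are conditional. This stands, and both should be stated with their condition. It does not rescue the claim: on the raw-score reading, power for 0.35 still falls short of 80% unless the correlation is about 0.81 or higher, and the documents offer no evidence for such a value.

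Third, the plan admits limited power. That admission is attached to the Aim 3 mediation question, not to the Aim 2 test.

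Fourth, Aim 2 is repeated with covariates. The power claim is for the one-way ANOVA, and the listed covariates do not include baseline FoR.

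Finally, no analysis becomes invalid. That is true; what is affected is the conclusion that a null result would support.

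**Conclusion.** The concern holds. The design effect of d = 0.70 is, on a common SD, twice the cited immediate effect and above the 3-month one, so calling the study conservatively powered is not supported by the evidence cited for it. On the change-score SD at two-sided 0.05 with all 100 patients analysed, power is 41% for d = 0.35 and 76% for d = 0.54. If g is on the raw-score SD, power for 0.35 depends on an unstated correlation and is below 80% unless that correlation is about 0.81 or more.

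A further uncertainty lies in the documents themselves: the Aim 2 text ties 0.35 to the health-worries subscale, while the power analysis presents it as FoR. Since both subscale and total scores are available, it is unclear which outcome the cited effect describes.

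**What to change.** Keep N = 100, the outcome and the test. In the power analysis:

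1. Delete the word conservatively and state that N = 100 gives 80% power for d of about 0.57 (f = 0.283) and 90% for d of about 0.65 (f = 0.327) on the change-score SD, before attrition. Add that, on that scale, power is about 41% at d = 0.35 and 76% at d = 0.54.
2. Name the SD by which the cited g is standardised. If it is the raw-score SD, give power over a range of assumed Time 1–Time 2 correlations (for g = 0.35, 31% to 78% over 0.3 to 0.8).
3. Reconcile whether 0.35 belongs to health worries or to FoR overall.

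In the Aim 2 text, say that a non-significant result does not by itself exclude an effect of the cited size, and report the effect with its 95% confidence interval (expected half-width about 0.40 change-score SD).

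The cost is a reworded paragraph and a short addition on interpretation and reporting. The only downside is a less favourable stated power.
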